9.2 Administration

The Investigational products will be taken orally by the subject during a period of 30 minutes - 1 hour.

Lumentin® 44

A volume of 1000 ml ± 200 ml shall be consumed. A steady intake rate of the contrast agent is recommended and the time period of intake should be 45 minutes - 1 hour.

The subject will be withdrawn from the trial if the maximum volume of the Investigational product taken by the subject is less than 750 mL.

There is no risk of overdose.

Diluted Omnipaque® and Movprep®

The volume of **Omnipaque® and Movprep®** consumed will be according to the standard of care praxis at the department of “Verksamhetsområde Bild och funktion Skånes Universitetssjukhus”. A steady intake rate of the contrast agent is recommended, and the time period of intake should be 30 minutes – 1 hour.

The subject will be withdrawn from the trial if the maximum volume of the Investigational product taken by the subject is below the recommended dose.

9.3 Packaging, Labelling and Storage

The Lumentin® 44 dispersion will be filled in 1.5L PET jars with white plastic screw-caps at Bioglan AB. The head-space above the dispersion will be filled with Argon gas, which is an inert gas that acts as preservative due to its antioxidant and antimicrobial properties.

The jars will be packed in aluminium laminated plastic bags which will be filled with argon and immediately sealed. The containers in their outer bags will be placed in a cardboard box to protect them during transport and storage.

All Lumentin® 44 dispersion supplies must be stored and transported under 2-8°C. Lumentin® 44 dispersion will be transported to the site upon request. Until final preparation and dispensing to the subjects, the Lumentin® 44 dispersion will be stored in a refrigerator, accessible to authorised personnel only.

Omnipaque® 240 mg I/mL and Movprep® will be stored in room temperature in a restricted area, accessible to authorised personnel only.

Packaging and labelling of the contrast agents will be performed by Bioglan AB in accordance with applicable regulatory requirements.

9.4 Blinding and Breaking the Blind

Not Applicable. The trial is an open label trial.

9.5 Drug Accountability

The Investigator is responsible for maintaining accurate investigational product accountability records throughout the trial.

Each dispensing of investigational product will be documented in the drug accountability log and the eCRF.

The height of the Lumentin® 44 foam in the PET jar will be measured prior to dispensing it to the subjects. The weight of all three contrast agents will be measured prior to dispensing as well as after intake. Height and weights will be and noted in the eCRF. Drug accountability will be carried out at regular intervals, as specified in the monitoring plan.

All unused investigational product (Lumentin® 44 dispersion) will be returned to Bioglan AB for destruction at the end of the trial. The Sponsor will be provided with the documentation of destruction of unused investigational product.

9.6 Drug Exposure and Compliance

All containers will be weighed before they are dispensed to the subject and again when returned by the subject and these weights (in gram) will be recorded in the eCRF.

Drug exposure will be estimated based on the weight of ingested contrast agent and the weight of the subject.

Data from this trial will be used to the extent possible for providing future advice as of how much Lumentin® 44 should be used in order to obtain CT-scan with good diagnostic readability.

The subject may be withdrawn from the trial if his/her wellbeing is jeopardised during intake of the contrast agent. The subject must be withdrawn if less than 750 mL of Lumentin® 44, or less than the, according to the general praxis of care, recommended dose of Omnipaque® and Movprep® can be consumed.

Details and procedures in case of subject withdrawal are described in Section 8.3.

9.7 Concomitant Medications

Concomitant Medication

Any medication the subject takes other than the investigational product (prescribed and over-the-counter-drugs) is considered a concomitant medication. All concomitant medications must be recorded in the eCRF. The following information must be recorded in the eCRF for each concomitant medication: generic name, route of administration, start date, stop date, dosage, and indication. Any changes in the dosage or regimen of a concomitant medication must be recorded in the eCRF.

At visit 1, CT-scan, subjects will be asked what medications they have taken during the last 2 weeks before visit 1, CT-scan.

At the contact 2, telephone interview, subjects will be asked what concomitant medications they are currently taking or have taken since they left the clinic.

All subjects will receive an intravenous injection of an iodine based contrast medium (Omnipaque® 350 mg I/mL) during the CT-scan examination. This is a standard of care procedure for all subjects undergoing a CT-scan at the clinic and is as such not part of the trial protocol defined procedures. The dose will be adjusted to body weight and kidney function and is usually given in the range of 60 to 115 ml of Omnipaque® 350 mg I/mL. The dose given and batch number of the Omnipaque® 350 mg I/mL will be noted in the eCRF.

Prohibited Previous and Concomitant Medication

All use of medication taken by oral route will be prohibited during 4 hours before taking the contrast agents and one hour post the intake.

All other medication taken by other routes are allowed.

10 PARAMETERS AND METHODS OF ASSESSMENT

10.1 Assessments of efficacy Parameters

10.1.1 Mean difference in contrast density

The contrast will be assessed by both the investigator and the sub-investigator, independently of each other, in the small bowel and expressed in Hounsfield Units (HU). The difference in contrast density between lumen and wall (mucosal lining) will be measured in 9 locations of the small bowel as described below.

The small bowel is divided in 5 sub-segments and defined as follows:

- Duodenum is defined as the first part of small bowel down to ligament of Treitz;
- Jejunum identified by its typical feathery mucosal pattern on Abd-CT
- The small bowel between the jejunum and terminal ileum is visually divided into two parts:
 - ⊖ Proximal ileum is approximately defined as 30 cm / 4 loops of small bowel following jejunum
 - ⊖ Distal ileum is approximately 30 cm / 4 loops proximal to terminal ileum
- Terminal ileum is defined as the last 15 cm of ileum mounding into the ileo-cecal valve

The difference in contrast density is measured in two sites in each of 4 of the defined sub-segments: duodenum, jejunum, proximal ileum, and distal ileum, and in the terminal ileum where (due to its shortness in length) only one site is selected.

Two regions of interest (ROI) measuring 6 mm in diameter will be selected by the investigator in the lumen of each segment except in the terminal ileum where only one region is selected. The ROIs will be placed where the lumen is best shown in the CT-image. The CT-scan software will provide a mean HU measurement of each of the selected ROIs and the values will be recorded by the investigator.

The HU of the wall will be set to +80HU as a standard for all measurements. It is not possible to discriminate between the lumen and the wall when Movprep® and Diluted Omnipaque® is used as contrast agents as they have a contrast similar to the wall contrast.

In each segment, the difference in contrast density between bowel lumen and wall will be calculated by subtracting the pin point HU value(s) of the wall (set to +80HU) from the mean ROI HU value(s) of the lumen. Two differences in contrast density values will thus be generated for each segment except in the terminal ileum where only one value is generated.

Each examination produced in the CT-scanner consist of more than 1 000 images which are stored in the patient's medical record. The investigator and the sub-investigator will independently select the best images on which contrast differences are calculated.

Screen-shots of all selected images will clearly identify sites of ROIs in the images, and an electronic footprint of storage time will be included in images when saved. Each image will also be uniquely identified by the CT-scanner's software. The images unique code and the time point they are saved will be entered in the eCRF, in order to document that the investigators are assessing the images independently. The investigators will also be given unique access codes to the eCRF so that they cannot access each other's assessment data.

The mean difference in contrast density in the small bowel is the sum of the differences in contrast density values (9 calculated values based on the observation of the investigator and 9 based on the sub-investigator observations, ie. in all 18 observations) divided by 18. All segments to which the contrast agent has not reached and thus, the contrast cannot be measured will not be included in the mean difference. The sum of the differences will in this case be divided by the number of measurable observations. The ability to fill the bowel will be investigated as a secondary objective, see below section 10.1.2.

10.1.2 Evaluation of ability to fill the bowel

The bowel filling agent will be distributed along the length of small bowel, i.e. the **extension**, but also cause a local widening of the bowel loop, **distension**. The filling of each of the 5 selected sub-segments of the small bowel in terms of extension and distension will be examined on the CT-scan by both the investigator and the sub-investigator, independently of each other, and graded using Likert scales between 1 and 9.

Subjects will be asked to fast for at least 4 hours prior to the intake of the contrast. The probability of the contrast agent to reach the terminal ileus is improved if the subject arrives fasted. Subject will be allowed to drink during the 4 hours.

The time point of assessment will be noted in the eCRF for both the investigator and the sub-investigator to document that the assessment has been done independently.

Extension scale:

1. no sign of contrast agent;
2. trace of contrast agent filling
3. segment filled to ca. 25%
4. segment filled to >25% but <50%
5. filled to segment filled to 50%
6. segment filled > 50% but <75%
7. segment filled to ca. 75%
8. segment filled to >75% but <100%
9. segment filled to 100%

The Extension score will be the sum of the grades both assessors and in each sub-segment and hence range from 10 to 90.

Distension scale:

1. no identifiable contrast agent
2. a minimal amount of contrast agent is identified
3. small amount of contrast agent, insufficient for placing a ROI of 6 mm
4. amount of contrast agent just allowing for a ROI of 6 mm
5. medium filled bowel loop
6. slightly better than grade 5
7. good filling
8. optimal filling
9. excellent or almost overdistended

The Distension score will be the sum of the grades both assessors and in each sub-segment and range from 10 to 90.

10.1.3 Diagnostic ability when examining Abd-CT

Diagnostic ability when examining Abd-CT will be assessed on the CT-scan by both the investigator and the sub-investigator, independently of each other.

The following features will be assessed:

- Small bowel appearance
- parenchymal organs, i.e. pancreas, ovaries, urinary bladder
- mesenterium and oment

using a Likert scales of 1-9 ranging, where:

1. impossible to observe details
5. medium
9. excellent resolution

The Diagnostic ability score will be the sum of the scores from both assessors and range from 6 to 54.

The time point of assessment will be noted in the eCRF for both the investigator and the sub-investigator to document that the assessment has been done independently.

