6.2 Secondary Objectives

- To describe and compare the ability of Lumentin® 44 to fill the bowel as compared to Movprep® and diluted Omnipaque®.
- To describe and assess how Lumentin® 44 influences reading of the abdominal CT-examination as compared to Movprep® and diluted Omnipaque® with respect to:
 - Diagnostics with particular regard to parenchymal organs, lymphatic system and tissue compartments beyond the gastrointestinal tract
- To investigate signs of degradation of Lumentin® 44 in terms of
 - Coalescence
 - Syneresis or drainage
- Describe and compare the ability to eat/drink for each of three contrast agents with respect to:
 - Taste
 - Smell
 - Consistency
 - Ability to swallow
 - Fullness
- Validity and repeatability of the primary endpoint
- To evaluate safety and tolerability after oral administration of each of three contrast agents

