7.2.2 Secondary Efficacy Variables

- Bowel filling properties (extension and distension) on Abd-CT in each of 5 selected sub-segments of the small bowel
- Degradation (presence of bubbles and signs of sedimentation) on Abd-CT in each of 5 sub-segments of the small bowel
- Diagnostic ability on Abd-CT of the parenchyma, lymphatic system and tissue compartments beyond the gastrointestinal tract.
- Subject assessments of taste, smell, consistency, ability to swallow and fullness after swallowing the contrast agent

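### The diagnostic ability score does not isolate or fully cover the variable it serves: small bowel appearance is one third of the sum, and the lymphatic system is not graded

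*Combined protocol and SAP*

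**What the plan says.** The secondary objective in section 6.2 is to describe and assess how Lumentin 44 affects the reading of the abdominal CT compared with the two comparators: "Diagnostics with particular regard to parenchymal organs, lymphatic system and tissue compartments beyond the gastrointestinal tract". The matching variable in section 7.2.2 lacks that qualifier and reads "Diagnostic ability on Abd-CT of the parenchyma, lymphatic system and tissue compartments beyond the gastrointestinal tract". The synopsis carries both statements.

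Section 10.1.3 says how the variable is measured. Three features are listed:

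- "Small bowel appearance"
- "parenchymal organs, i.e. pancreas, ovaries, urinary bladder"
- "mesenterium and oment"

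They are graded "using a Likert scales of 1-9 ranging" and "assessed on the CT-scan by both the investigator and the sub-investigator", each working independently. The result is a single number: "The Diagnostic ability score will be the sum of the scores from both assessors and range from 6 to 54".

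Section 13.4.2 gives secondary objectives the same treatment as the primary, which under section 13.4.1 is a Wilcoxon rank sum test at the two-sided 5% level. No feature-level analysis and no subscore for structures outside the bowel is specified.

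**The concern.** The variable is about what can be read outside the gastrointestinal tract, but a third of the score is about what can be read inside it. That third is not neutral between arms. Section 5.2 presents better lumen-to-wall contrast as the product's purpose, and section 7.1 says the readers can recognise the agent from the image. Meanwhile one of the three named targets, the lymphatic system, has no rating of its own.

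The population makes this matter more. Referral for small bowel disease is an exclusion criterion, section 7.3.1 says the trial is not designed to study such disease, and patients are also recruited through oncology departments. For these patients the clinical question lies mainly outside the bowel. If only the sum is tested, a favourable result may be nothing more than the bowel effect, and an indifferent result may be a bowel gain cancelling a loss elsewhere. In neither case does the planned analysis answer the question in section 7.2.2.

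**Working it through.** **1. Reproduce the stated range.** Range = features × readers × (1 to 9). With 3 features and 2 readers: 3 × 2 × 1 = 6 and 3 × 2 × 9 = 54, which matches section 10.1.3 exactly. Two non-bowel features would give 4 to 36, and all three plus a lymphatic feature 8 to 72. The stated 6–54, with the features listed, therefore has small bowel in and lymphatics out.

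**2. Compare the targets with the ratings.**

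| Target in section 7.2.2 | Feature in section 10.1.3 |
|---|---|
| Parenchyma | Parenchymal organs |
| Lymphatic system | None |
| Compartments beyond the tract | Mesentery and omentum |
| Not a target | Small bowel appearance |

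Small bowel supplies 2 of the 6 ratings, or 2 to 18 of the 6 to 54 points. The non-bowel features supply 4 of the 6.

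**3. Offsetting.** If the bowel, organ and mesentery grades shift by b, o and m for both readers, the sum shifts by 2b + 2o + 2m. Let every comparator rating be 5, so the total is 6 × 5 = 30 and the non-bowel part is 4 × 5 = 20.

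- b = +2, o = m = −1: total 2 × 7 + 4 × 4 = 30; non-bowel part 16.
- b = +4, o = m = −2: total 2 × 9 + 4 × 3 = 30; non-bowel part 12.
- b = +2, o = m = 0: total 2 × 7 + 4 × 5 = 34; non-bowel part still 20.

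The first two cases hide a loss. The third shows a gain that owes nothing to the structures named in the variable.

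**4. Size in a trial of this kind.** The documents give no SD, effect size or between-item correlation for these grades, so the following are assumptions: between-subject SD 1.2 to 2.0, reader SD 0.6, item correlation 0 to 0.5, comparator mean grade 5 to 6, grades rounded and held within 1 to 9. Each comparison has 40 v 20 subjects (synopsis and section 8.4; section 8.5 states 1:1:1 instead) and uses a two-sided Wilcoxon test at 5%.

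| Between-subject SD | Item correlation | Bowel +2, others −1: loss shown by non-bowel items | Bowel +2, others 0: sum shows superiority |
|---|---|---|---|
| 1.2 | 0 | about 96–97% | about 83–87% |
| 1.2 | 0.5 | about 88–90% | about 61% |
| 2.0 | 0.5 | about 49–52% | about 28% |

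In the +2/−1 scenario the planned sum is significant in about 4–6% of trials throughout, as it must be when its expected shift is zero. The lower ends move by a few points with baseline grade and simulation error.

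A second variance set-up, with independent items and total per-rating SD of 1.0, 1.5 or 2.0, gives about 5% for the sum and about 100%, 96% and 81% for the non-bowel items.

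**The case against.** The strongest reply is that the score is a defensible measure of overall reading. The objective in section 6.2 places emphasis on the listed structures without excluding others, and section 5.2 describes the pilot result in terms of the examination as a whole. Four of six ratings do lie outside the bowel. A reader might infer that the score does not measure the objective at all, and that goes too far. But the variable in section 7.2.2 has no softening words, and neither place mentions the bowel as a target, so the mismatch stands.

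A reader might also infer that this score is the trial's test of no harm to the rest of the reading, and that the plan would declare no harm wrongly. The documents set no margin, non-inferiority test or decision rule for it. A non-significant test of equality would not support such a claim, and nothing shows that a loss outside the bowel is likely; the pilot reported easy acceptance by the radiologist.

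Offsetting is not general either. With no bowel gain and a 1-grade loss elsewhere, the sum shifts by −4 and detects it in about 89% of trials at SD 1.2 with independent items. It takes a bowel gain of about twice the loss per feature to cancel it fully.

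Naming ovaries might suggest that men cannot be scored. The 6–54 range shows that the organs form one combined rating per reader, so no missing score follows.

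Finally, much is recoverable. The features are graded separately, the images are stored, and section 13 allows a later SAP. That lowers the consequence but does not remove the gap: the SAP is optional, and a split chosen after the sum is known is weaker than a planned one. Nor do the documents say that lymph nodes are graded under the mesentery feature.

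**Conclusion.** The point holds as a mismatch between variable and score. The score does not isolate reading beyond the gastrointestinal tract, because one third of it is small bowel appearance, and it does not fully cover that reading, because nothing grades the lymphatic system. Both facts come directly from sections 7.2.2 and 10.1.3 and need no assumption. Nor does the offsetting: it follows from an unweighted sum.

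The percentages are different in kind. They illustrate what the sum could do under chosen effects and assumed variability. They are not predictions, and the wide spans (about 49–97% and 28–87%) show how far they depend on the SD and on the correlation between features graded by the same reader on the same scan. This is one of several secondary variables in a phase II trial without multiplicity adjustment, so the issue should be corrected but does not threaten the primary analysis.

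**What to change.** Before any data are seen, amend sections 6.2, 7.2.2 and 10.1.3 and the synopsis together:

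1. Define the score for this variable as the sum of the non-bowel features only: 2 features × 2 readers, range 2 × 2 × 1 = 4 to 2 × 2 × 9 = 36.
2. Report small bowel appearance as a separate variable, with its own comparison.
3. Either add one 1–9 rating of the lymphatic system per reader, giving 3 × 2 × 1 = 6 to 3 × 2 × 9 = 54, or remove the lymphatic system from the objective and the variable. If the rating is added, the range is again 6–54 with different content, so the features summed should be listed explicitly.

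The split costs only wording, since the ratings are already planned. The lymphatic item costs one extra rating per reader on images already being read, plus an eCRF field. No extra scan, reader or subject is needed.

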10.1.4 Degradation of contrast agents

Degradation of Lumentin® 44 is founded on the two characteristics Coalescence and syneresis or drainage.

Coalescence:

0. No bubbles visually detectable at the CT-scan
1. Bubbles visually detectable at the CT-scan

Syneresis or drainage:

0. No syneresis or drainage, i.e. separation of air and liquid phases, observed
1. Syneresis or drainage observed

Sign of degradation will be assessed on the CT-scan, by both the investigator and the sub-investigator, independently of each other, in each of the 5 selected sub-segments of the small bowel.

Degradation of contrast agents score will be the sum of the scores from both assessors and in each sub-segment and range from 0 to 20.

The time point of assessment will be noted in the eCRF for both the investigator and the sub-investigator to document that the assessment has been done independently.

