13.4.2 Secondary Efficacy Analysis

The secondary efficacy objectives will be analysed using the same principles and methods as the primary efficacy objectives.

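### The degradation score makes no allowance for segments the foam did not reach, so incomplete filling lowers it, and the blanket rule in 13.4.2 conflicts with an objective limited to Lumentin 44

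*Combined protocol and SAP*

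**What the plan says.** Section 10.1.4 defines two signs, each graded 0 or 1. Grade 0 for coalescence is "No bubbles visually detectable at the CT-scan". Grade 0 for syneresis or drainage is "No syneresis or drainage, i.e. separation of air and liquid phases, observed". Both readers grade both signs "in each of the 5 selected sub-segments of the small bowel", with no condition that the agent is present there. The total is then formed: "Degradation of contrast agents score will be the sum of the scores from both assessors and in each sub-segment". Its stated limits are 0 and 20.

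Unreached segments are foreseen elsewhere. For the primary variable, section 10.1.1 states: "All segments to which the contrast agent has not reached and thus, the contrast cannot be measured will not be included in the mean difference". Its divisor becomes the number of measurable observations. In section 10.1.2 the lowest extension grade, 1, is reserved for a segment in which no agent is seen.

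On analysis, section 13.4.2 says: "The secondary efficacy objectives will be analysed using the same principles and methods as the primary efficacy objectives". Under 13.4.1 those methods are Wilcoxon rank sum tests of Lumentin 44 against each comparator. Section 7.2.2 lists degradation among the secondary efficacy variables without restricting it to an arm. The objective in section 6.2, however, reads "To investigate signs of degradation of Lumentin® 44 in terms of" coalescence and syneresis or drainage. It names one agent and asks for no comparison, whereas the filling and drinking objectives in the same list do ask for one.

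**The concern.** Section 7.3.1 gives the stability of Lumentin 44 after administration as one of the things the secondary objectives are meant to show. A plain sum over all five segments mixes that with a second quantity, how far the foam travelled. An empty segment fits the wording of grade 0 on both signs, so a low total can mean stable foam throughout or foam that reached few segments. At stake is the reading of this variable: a subject with poor filling would look like a subject with stable foam.

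The second issue is the comparison. Separation of air and liquid phases is a property of a foam, and the comparators are liquids. If the general rule for secondary objectives is applied as written, the report will carry p-values for degradation that mostly restate which agent is the foam.

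**Working it through.** **Inputs.** From 10.1.4: 2 signs, 2 readers, 5 segments, each item 0 or 1. From 8.4: 40 evaluable subjects on Lumentin 44 and 20 on each comparator. The documents give no degradation rate and no distribution of segments reached, so those are assumed below and varied.

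**1. The plan's own range.** 2 signs × 2 readers × 5 segments = 20 items, so the score runs from 0 to 20. This agrees with 10.1.4.

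**2. Effect of reach on the ceiling.** Let k be the number of segments reached. An unreached segment adds 0 if graded 0. If it is left blank, and observed cases are used without substitution (13.2), it also adds 0. The maximum is therefore 2 × 2 × k = 4k: 20, 16, 12, 8, 4 and 0 for k = 5 to 0. This needs no assumed rate, only that no reader marks a sign where there is no agent. A subject with no segment reached scores 0, the best value. As an example, a score of 4 can be 4 of 20 signs (20%) with five segments reached or 4 of 4 signs (100%) with one reached.

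**3. Effect on the expected score.** With the same rate r for every sign in every segment, the expected score is 4kr:

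| k reached | r = 0.2 | r = 0.3 | r = 0.5 | Share of full value |
|---|---|---|---|---|
| 5 | 4.0 | 6.0 | 10.0 | 100% |
| 4 | 3.2 | 4.8 | 8.0 | 80% |
| 3 | 2.4 | 3.6 | 6.0 | 60% |
| 2 | 1.6 | 2.4 | 4.0 | 40% |

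The share is k/5 whatever r is. Three segments reached means 40% lower, with identical degradation where foam is present.

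**4. Sum against proportion.** Two hypothetical groups of 40 and 20 were simulated with equal r, with foam reaching 3 segments in the first and 5 in the second (4,000 runs, independent signs). The plain sum gave Wilcoxon p < 0.05 in 93%, 99% and 100% of runs at r = 0.2, 0.3 and 0.5, with the lower mean in the worse-filled group. The proportion of assessable signs gave 5.2%, 4.7% and 3.9%, near the nominal 5%. This contrast in reach is deliberately strong. It shows how the score behaves and does not forecast the trial.

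**5. Foam against liquid.** Assume every comparator subject scores 0. Then 8 of 40 Lumentin 44 subjects (20%) with any non-zero score are enough for a two-sided p of 0.035 against 20 zeros. With r = 0.01 per item the test rejects in 43% of runs, and with r = 0.02 in 97%. Even very rare degradation would give a significant difference.

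**The case against.** Several points on the other side are fair.

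- A reader might infer that the plan instructs readers to score unreached segments as 0. It does not; no rule is given. The defect survives because grading 0 and leaving blank give the same sum. Only setting the whole subject's score to missing would avoid it, and no section says to do that.
- A reader might infer that a between-arm test of degradation is firmly planned. It follows only from the general sentence in 13.4.2, and 6.2 points the other way. Section 13 also leaves detailed methods to a possible separate SAP. What stands is a conflict that needs wording.
- A reader might call the comparison meaningless. That goes too far: visible bubbles can be graded in any arm, and comparator grades could show background gas. The test would be weakly informative.
- A reader might add that distal segments are where degradation matters most. The documents do not say so; the stability requirement in 5.2 concerns passage through the upper gastrointestinal tract.
- Frequent loss of segments is not shown. Sections 5.2 and 7.3.1 report that the pilot foam filled the whole small bowel, though with a 60% air formulation rather than 44%. This limits how large the effect may be in practice. It does not supply the missing rule, and 10.1.1 treats unreached segments as a real possibility.
- Section 7.2.2 defines the variable segment by segment, and extension is graded in the same segments by the same readers. A careful analyst could therefore interpret a zero. That shows the correction is easy, but the prespecified total does not use the information.

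**Conclusion.** The point holds for a secondary variable and should be settled before analysis. As defined, the total is capped at 4 times the number of segments reached. Under an equal sign rate in all segments, its expected value falls to k/5 of the full value. Incomplete filling therefore lowers apparent degradation. If unreached segments would have degraded more than the others, the shortfall is larger; if less, smaller. How often it occurs cannot be judged from the documents.

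Sections 13.4.2 and 6.2 disagree on whether degradation is compared between arms. If it were tested, the result would mainly reflect foam versus liquid; the figures for that rest on the assumption that the liquid arms score 0. Trial success depends only on the two primary comparisons in 13.4.1, so the primary analysis and the sample size are untouched.

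**What to change.** In the SAP, or by amending 10.1.4 and 13.4.2:

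1. Treat a segment as not assessable for a reader who gave it extension grade 1. Prespecify that cut-off, and add a sensitivity analysis at a stricter one, because a trace of agent may be too little to judge drainage.
2. Express degradation as positive signs divided by assessable signs, overall and per segment, and show the number of assessable segments beside it. A subject with no assessable segment has no proportion and should be counted as such.
3. Compute 95% confidence intervals at subject level, for example for the mean subject proportion or by a bootstrap over subjects, because up to 20 signs are clustered within one subject.
4. State in 13.4.2 that degradation is descriptive for the Lumentin 44 arm and exempt from the between-arm tests.

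The cost is SAP wording and derivation code; the extension grades are already collected. One downside remains: foam that has collapsed completely might be graded as no agent present and so be excluded. Reporting the count of not-assessable segments keeps that visible.
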